## **Background**

**Importance:** Medication nonadherence results in poor clinical outcomes and increased healthcare spending. Although specialty pharmacies tend to have high adherence rates, resources are needed to address the unique barriers associated with nonadherence to specialty medications.

**Objective:** A QI study was conducted to evaluate a service designed to address patient-specific reasons for nonadherence to improve specialty medication adherence at Vanderbilt Specialty Pharmacy. This is a retrospective review of the data collected during the QI study. As results of the QI study were positive and we believe our findings to be generalizable for other specialty pharmacies to implement, we plan to analyze and report the results of the previously collected data.

**Design:** A quality improvement study using a pragmatic, randomized controlled design, was conducted from May 2019 and August 2021. Eligible patients were randomized 1:1 to usual care or intervention arms and stratified by historical rates of nonadherence in their clinic. Intervention patients underwent a baseline adherence assessment to identify reasons for nonadherence and received patient-tailored interventions and 8 months of follow up from a specialty pharmacist. A Wilcoxon test was used to test the difference in 6, 8, and 12-month post-enrollment PDCs between the intervention and usual care arms.

**Main Outcomes and Measures:** The primary outcome of the QI study was PDC calculated at 8-months post-enrollment. An exploratory analysis evaluated PDC at 6-months and 12-months post-enrollment. While the QI study was conducted to improve service at Vanderbilt, our findings suggest that any specialty pharmacies could improve adherence with existing resources.

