## **Inclusion/Exclusion Criteria**

All data will be obtained retrospectively. All nonadherent patients will be included in the QI project and patients with 2 or more refills in the study period will be included in the data analysis.

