## **Risks**

The only potential risk is breach of data which is stored in a HIPAA-secured REDCap and only deidentified data was extracted for analysis. As data has already been extracted and stored in REDCap and deidentified data extracted for analysis, there is minimal risk to the current retrospective review request.

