## **Privacy/Confidentiality Issues**

Data was collected as part of the QI study and is already stored in REDCap. No additional data will be collected. All data will remain in the REDCap. Only KSP will have access to the data.

Patient data is stored in the REDCap (a HIPAA-compliant web-based application) and only accessible to KSP. Access is granted as either able to view patient information or not so for example, our statisticians never see any patient-specific information.

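### Is the exploratory 12-month PDC misleading because it may contain the whole 8-month service period?

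*Protocol*

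**What the plan says.** The Design paragraph of the protocol's Background states that intervention patients "received patient-tailored interventions and 8 months of follow up from a specialty pharmacist". Under Main Outcomes and Measures, "The primary outcome of the QI study was PDC calculated at 8-months post-enrollment", and for the other two time points "An exploratory analysis evaluated PDC at 6-months and 12-months post-enrollment". One test serves all three: "A Wilcoxon test was used to test the difference in 6, 8, and 12-month post-enrollment PDCs between the intervention and usual care arms".

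Neither document defines the PDC interval: there is no start day, end day or denominator, and no statement on whether the measure is cumulative, trailing or fill-to-fill. The start of the 8 months of follow-up relative to enrollment is not given either. No comparison restricted to the months after the service is planned.

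The SAP tests each outcome separately at the two-sided 5% level, promises 95% confidence intervals for every treatment effect, and treats secondary and exploratory analyses as a supplement to the primary evidence. Its analysis set requires at least two refills after enrollment. Neither document mentions persistence of effect, or treats the three time points as separate confirmations.

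**The concern.** The 12-month PDC is the only planned measure that reaches past the end of the service. A reader may naturally take a significant 12-month difference as evidence that the benefit continued once the pharmacist stopped calling. If PDC is cumulative, that inference fails, because most of the 12-month window is the service period itself. The 6-month window would likewise sit inside the primary one, so three significant tests could look like three confirmations when they share most of their data.

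Durability matters to a pharmacy deciding whether to adopt such a service, and the named test does not isolate it. Wilcoxon p-values, or medians, at 8 and 12 months cannot be subtracted to give the effect in months 9 to 12.

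**Working it through.** The documents give no sample size, SD, effect size or correlation, so there is no planned figure to reproduce.

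**Inputs from the documents:** an 8-month service; PDC at 6, 8 and 12 months; two-sided 5% tests; 1:1 allocation.

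**Assumptions:** PDC accumulates from enrollment over fixed windows (8 months = 243 days, 12 months = 365 days), and the service starts at or near enrollment.

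**1. Dilution.** Write D8, D12 and D9–12 for the mean differences between arms in each window.

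D12 = (243 × D8 + 122 × D9–12) / 365

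If the effect is zero after month 8, D12 = (243/365) × D8 = 0.67 × D8.
- D8 of 6 points: 0.06 × 243/365 = 0.040.
- D8 of 10 points: 0.10 × 243/365 = 0.067.

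Conversely, with weights 8/12 and 4/12, a D12 of 0.05 fits a lasting effect of 0.05, and equally an effect of 0.05 × 1.5 = 0.075 that ended at month 8.

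**2. Can the test separate the two?** A Wilcoxon simulation used assumed inputs: 200 per arm, usual-care PDC centred near 0.78, between-patient SD 0.15, values capped to 0–1, and 2,000 runs per scenario.

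| Scenario | Mean D12 | Rejection |
|---|---|---|
| Nominal 0.06, lasting | 0.051 | 94% |
| Nominal 0.09, ends at month 8 | 0.050 | 93% |
| No effect | 0.000 | 4.7% |

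The first two rows are indistinguishable on the 12-month result alone.

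**3. Reading 8 and 12 months together.** Rearranging step 1:

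D9–12 = (365 × D12 − 243 × D8) / 122, or about 3 × D12 − 2 × D8

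With D8 = 0.06 and D12 = 0.050: (18.25 − 14.58)/122 = 0.03, which is half the effect persisting. This needs mean differences and fixed denominators. It fails for a fill-to-fill PDC. A patient with no fill after month 8 and 0.90 at both times gives (365 × 0.90 − 243 × 0.90)/122 = 0.90, although nothing was filled in those months.

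**4. What a months 9–12 comparison would deliver.** Take exchangeable monthly values with correlation ρ, so that the variance of a k-month mean is proportional to V(k) = (1 + (k − 1)ρ)/k.
- SD ratio to the 8-month PDC at ρ = 0.3: V(4) = 1.9/4 = 0.475 and V(8) = 3.1/8 = 0.3875; √(0.475/0.3875) = 1.107.
- SD ratio at ρ = 0.7: √(0.775/0.7375) = 1.025.
- With 80% power at 8 months, the standardised effect is 1.960 + 0.842 = 2.802. Under full persistence, the months 9–12 test rejects in 72% (ρ = 0.3) to 78% (ρ = 0.7) of trials. It therefore misses a fully lasting effect in 22–28%.
- The 95% CI half-width, as a multiple of the 8-month effect, is 1.960/2.802 × 1.107 = 0.77 at ρ = 0.3 and 1.960/2.802 × 1.025 = 0.72 at ρ = 0.7.

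**5. Carry-over.** A fill on day 240 with a 30-day supply lasts to day 269 and covers 269 − 243 = 26 of 122 days (21%). With a 90-day supply it lasts to day 329 and covers 86 of 122 (70%). The supply lengths are assumed. How supply dispensed before month 9 is counted could therefore shape the result.

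**The case for a change.** The best case for a change is that it looks cheap. Defining the PDC window takes a sentence, and so does a note that the 12-month measure overlaps the primary one. The protocol hopes that other specialty pharmacies will adopt the service, and for them it matters whether the gain outlasts the service. The SAP wants its supplementary analyses to give a fuller picture of the treatment effect, and a post-service comparison would do that. The retrospective review states that "No additional data will be collected", and none would be needed if fill dates are in the extract.

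Part of this stands. The window is undefined, and under the cumulative reading the 12-month PDC alone does not speak to durability. The recovery in step 3 is not guaranteed either, because the SAP promises confidence intervals without naming the estimator.

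The rest is weaker. The overlap is conditional: if the 12-month PDC is a trailing measure over the months after the service, the point disappears. The 12-month result will also be read beside the 8-month primary, not alone. A months 9–12 analysis would be chosen after the outcome was known, since the protocol writes "As results of the QI study were positive". The documents do not say whether fill dates were kept; they say only that "only deidentified data was extracted for analysis". The entry rule, "patients with 2 or more refills in the study period will be included in the data analysis", does not guarantee any fill in months 9 to 12, so stopping, switching or leaving the pharmacy would weigh more heavily there than in the primary outcome.

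**Conclusion.** No change to the plan follows. The arithmetic is right: with cumulative windows starting at enrollment, two thirds of the 12-month PDC is service time, and an effect that ended at month 8 keeps 0.67 of its size. That limits how an exploratory result can be read; it is not a fault in any planned analysis. The plan asks whether adding the service raises adherence, and the 8-month comparison answers that whichever way the 12-month figure is interpreted.

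Two things remain. The first is missing detail: the analysts must fix a start, an end and a denominator to compute PDC at all, and reporting these, with the overlap that results, is ordinary practice. The second is a fair trade-off: a months 9–12 comparison would isolate the post-service period, but with the imprecision and carry-over sensitivity shown above, and after the results were known. Statisticians could reasonably differ on whether it is worth running.

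The 0.67 factor depends only on the assumed windows and service start. The rejection rates and interval widths rest on assumed power, correlation and simulation inputs and are illustrative. The judgement would change if a report drew a claim of lasting benefit from the 12-month PDC alone; neither document does so.

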## **Rationale and Specific Aims**

Integrated health system specialty pharmacies provide a high-touch service to their patients at baseline. Our QI study aimed to find out if adding an additional adherence service could identify and address patient-specific reasons for nonadherence to increase adherence to specialty medications at VUMC. Few studies report the reasons for nonadherence to specialty medications. It is commonly accepted that cost is a large reason for nonadherence; however, integrated specialty pharmacies provide financial services to minimize and often remove the impact of cost. In the QI study, we collected each patient's reason for nonadherence by reviewing their chart and by asking the patient (in the intervention arm). Before this study, it was unknown what the reasons for nonadherence were in a broad specialty disease population and if those reasons could be addressed by a pharmacist. The findings of our QI study will be helpful to other specialty pharmacies as it demonstrated that non-labor-intensive interventions could have a significant impact on specialty medication adherence.

## **Inclusion/Exclusion Criteria**

All data will be obtained retrospectively. All nonadherent patients will be included in the QI project and patients with 2 or more refills in the study period will be included in the data analysis.

## **Study Procedures**

This is a retrospective review of data collected under IRB #181452.

## **Risks**

The only potential risk is breach of data which is stored in a HIPAA-secured REDCap and only deidentified data was extracted for analysis. As data has already been extracted and stored in REDCap and deidentified data extracted for analysis, there is minimal risk to the current retrospective review request.

## **Reporting of Adverse Events or Unanticipated Problems involving Risk to Participants or Others**

Adverse events (which may include breach of confidentiality) which are serious, unanticipated, and related (or possibly related) to the research procedures will be reported to the IRB within 7 calendar days of the Investigator's knowledge of the event.

## **Privacy/Confidentiality Issues**

Data was collected as part of the QI study and is already stored in REDCap. No additional data will be collected. All data will remain in the REDCap. Only KSP will have access to the data.

Patient data is stored in the REDCap (a HIPAA-compliant web-based application) and only accessible to KSP. Access is granted as either able to view patient information or not so for example, our statisticians never see any patient-specific information.

## **Follow-up and Record Retention**

Data will be destroyed no earlier than 3 years from the date the research is closed with the IRB.

**Patient-centered services to improve specialty medication adherence: results from a prospective randomized controlled trial**

NCT03709277

Protocol Date: 08/17/2022

All outcomes and analyses are prospectively characterized as primary or secondary.

This is a superiority trial with intervention expected to yield superior outcomes, compared to control. However, all outcomes will be tested independently at the two-tailed 5% significance level. All estimates of treatment effects will be presented with 95% confidence intervals.

No formal adjustments will be undertaken to constrain the Type I error associated with planned secondary or exploratory analyses. The information provided by analyses is designed to supplement the evidence from the primary analyses; it will provide a more complete characterization of the treatment effects.

The analyses for all quantitative outcome measures will be conducted on an intention to treat (ITT) basis, i.e. all participants will be analyzed in the trial phase (control or intervention) in which they were recruited, regardless of whether their treatment adhered to the trial protocol or not, assuming they have enough information to calculate the outcome. The ITT strategy for this trial is based on the following principles:

- All available outcome data are collected on all recruited participants
- For the ITT analysis, the outcomes for each participant having at least 2 post-enrollment medication refills (required for primary outcome calculation) will be included in the data for the trial phase (control/intervention) in which the participant was recruited.
- The primary analyses will be reported for all participants having 2 medication refills post-enrollment. If the amount of missing data exceeds 10% at the primary endpoint, missing data will be imputed under the assumption that data is missing at random.

All analyses will be conducted using the R Statistical Programming Language 4.0.2 after data collection is completed.

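### The analysis labelled intention-to-treat keeps only patients with at least 2 post-enrollment refills, a subset formed after randomisation; bias of unknown size and direction is possible, and the imputation clause does not repair it

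*SAP*

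**What the plan says.** The Protocol (Background) describes 1:1 randomisation to usual care or to a service whose patients "received patient-tailored interventions and 8 months of follow up from a specialty pharmacist". The primary outcome is PDC at 8 months after enrollment, and the arms are compared with a Wilcoxon test.

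Under Inclusion/Exclusion Criteria the Protocol says "All nonadherent patients will be included in the QI project", but then "patients with 2 or more refills in the study period will be included in the data analysis".

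The SAP labels the analysis ITT with the qualifier "assuming they have enough information to calculate the outcome". Its bulleted ITT principles are:

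- First: "All available outcome data are collected on all recruited participants".
- Second: "the outcomes for each participant having at least 2 post-enrollment medication refills (required for primary outcome calculation) will be included in the data".
- Third: "The primary analyses will be reported for all participants having 2 medication refills post-enrollment". It then adds a conditional rule: where missingness "exceeds 10% at the primary endpoint, missing data will be imputed under the assumption that data is missing at random".

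The supplied documents describe no PDC formula, days' supply, sample size, number of patients with fewer than 2 refills, table of exclusions by arm, or analysis of all randomised patients.

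**The concern.** Whether a patient reaches two refills is known only after randomisation. It is a component of PDC, and the service works on it over the same 8 months in which the primary outcome accrues. Selecting on it removes the patients who refilled least, and it may remove different numbers or different kinds of patients from each arm. Randomisation protects a comparison of everyone randomised. It does not protect a comparison of those who went on to refill twice.

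The set is also not fully defined. The Protocol counts refills over the study period and the SAP counts them after enrollment. Neither says whether both refills must fall within the 8 months.

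At stake is what the primary result means. A reader who sees the ITT label will take the difference as the effect in all randomised patients, and the Protocol offers the findings to other specialty pharmacies.

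**Working it through.** There is no plan figure to reproduce, because the documents give no sample size, effect size or exclusion count. All inputs below are assumed, and they serve only to show what the rule can do.

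**Identity.** In one arm let p be the share with fewer than 2 refills, R the mean PDC of those with at least 2, and L the mean PDC of the rest. The all-randomised mean is (1-p)R + pL = R - p(R-L). With U for usual care and S for service:

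all-randomised difference minus restricted difference = pU(RU-LU) - pS(RS-LS).

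This holds for any PDC defined for every patient. The gap is zero only if the two terms are equal, so it depends on who is excluded as well as how many.

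**Assumed inputs.** PDC is over a fixed 240-day window. Patients who continue in either arm have mean c = 0.80, plus a gain g in the service arm. Patients who reach two refills only in the arm with fewer exclusions have r = 0.50. One 30-day fill gives 30/240 = 0.125, so an even mix of 0 and 1 fill gives L = 0.0625. With m the larger of the two exclusion shares:

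- all-randomised mean = (1-m)c + (m-p)r + pL
- restricted mean = [(1-m)c + (m-p)r]/(1-p)

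**Worked case, 15% vs 5% excluded, g = 0.**

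- Usual care: all = 0.85×0.80 + 0.15×0.0625 = 0.6894; restricted = 0.80.
- Service: all = 0.68 + 0.10×0.50 + 0.05×0.0625 = 0.7331; restricted = 0.73/0.95 = 0.7684.
- Differences: all-randomised +4.4 points, restricted -3.2 points.
- Identity: 0.15×0.7375 - 0.05×0.7059 = 0.0753, which equals 0.0438 + 0.0316 apart from rounding.

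| Excluded, usual care vs service | Gain g (points) | All-randomised | Restricted | Effect of the rule |
|---|---|---|---|---|
| 15% vs 5% | 0 | +4.4 | -3.2 | reversed against the service |
| 15% vs 5% | 6 | +9.5 | +2.2 | shrunk |
| 5% vs 2% | 0 | +1.3 | -0.9 | reversed, small |
| 5% vs 15% | 0 | -4.4 | +3.2 | reversed in favour of the service |
| 10% vs 9% | 10 | +9.44 | +9.56 | slightly inflated |
| 10% vs 10% | 3.5 | +3.15 | +3.5 | slightly inflated |
| 10% vs 10%, different kinds excluded* | 0 | -7.4 | 0 | harm hidden |

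*Usual-care leavers transferred elsewhere and are truly at 0.80; service leavers are truly at 0.0625. The truth is (0.9×0.80 + 0.1×0.0625) - 0.80 = -0.074.

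If every excluded patient had one 90-day fill (L = 90/240 = 0.375), the first row becomes +1.25 against -3.2, a gap of 4.4 points instead of 7.5.

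**Type I error.** A simulation with 8 monthly fill opportunities and 200 patients per arm (both assumed) gave, with no effect on refilling, Wilcoxon rejection rates of 4.9% on all randomised patients and 5.1% on the restricted set. When more low fillers stopped early in the service arm (5.8% vs 14.2% excluded), the differences were -2.5 points for all randomised patients and +3.0 restricted. Rejection rates were 7.9% and 20.4%.

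**Imputation clause.** There are two readings.

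- *Patients with 0 or 1 refill do not count as missing.* Every analysed patient already has the two refills said to be needed, so the clause never reaches those left out.
- *They do count as missing.* The clause acts only above 10%. With equal arms, 15% and 5% pool to 10%, which does not exceed it; 15% and 10% pool to 12.5%, which does; 5% and 2% pool to 3.5%. When it acts, it predicts non-refillers from refillers, although low refilling is what made the value missing. With no informative predictor, each arm's imputed mean equals its restricted mean, and the worked case stays at -3.2.

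**The case against.** The strongest defence has five parts.

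1. *The restriction is disclosed, and both documents apply a two-refill rule.* True. The fault is therefore the label and the missing all-randomised analysis, not concealment.
2. *Two refills are needed to calculate PDC.* This stands in part. A fixed window from enrollment would give a value with 0 or 1 fill, so the SAP's wording may point to a PDC measured from fill to fill. In that case L is undefined and the figures above do not apply. The selection remains, because patients without a value still drop out for a post-randomisation reason.
3. *Nothing suggests that exclusions differ by arm.* True, but the supplied documents describe no counts that would show it either way. The data were collected under a separate IRB approval (Protocol, Study Procedures) whose protocol was not supplied, so the counts and the PDC formula may exist there.
4. *The clause for more than 10% missing covers it.* It does not, on either reading.
5. *The rule is conservative.* A reader might infer that better retention under the service always makes the rule work against it, or that false favour needs more exclusions in the service arm. Neither holds: the 10% vs 9% row improves retention and is still slightly inflated, and the last row hides harm at equal exclusion rates.

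A reader might also infer that the positive results mentioned in the Protocol are a product of this rule. The documents do not support that, since no exclusion numbers are given and the bias could be small, absent or in the other direction.

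**Conclusion.** The point holds. The primary comparison is of a post-randomisation subset and should not be called ITT. This follows from the text and needs no assumed number.

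The size and direction of any bias cannot be determined. In the illustrations the gap between the two differences ranges from about 0.1 to 7.5 points, and the rule can shrink, inflate or reverse the effect. These figures rest on an assumed fixed-window PDC and assumed exclusion shares; they are not estimates for this trial. With no effect on refilling, the test keeps its level near 5%. Because the actual exclusions are unknown, this should be fixed, but it is not shown to overturn the result.

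**What to change.** 1. Stop calling the set ITT. Describe it as the analysis of patients with at least 2 refills, and use one counting window in the Protocol's Inclusion/Exclusion Criteria and in the SAP.
2. Report by arm the number randomised and the numbers with 0 and with 1 refill. Add reasons from chart review where already recorded, taken the same way in both arms, because only intervention patients were asked directly (Protocol, Rationale and Specific Aims).
3. Add a sensitivity analysis of all randomised patients by randomised arm, disclosed as post hoc. Give patients with 0 or 1 refill the lowest ranks in the planned Wilcoxon test. If dispensing data for them are already held, 8-month PDC over a fixed window from enrollment may be used instead. State which version was used.
4. Do not impute patients with 0 or 1 refill from those with 2 or more, and say who counts as missing for the 10% clause. Where reasons are already recorded, vary how transfers, prescriber stops and deaths are scored.

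**Cost.** Wording, one table and one extra analysis; the planned analysis stays. The Protocol (Privacy/Confidentiality Issues) rules out further data collection. The lowest-rank version needs only the counts in item 2. Varying the scoring in item 4 needs recorded reasons for each patient, and the PDC version needs dispensing records that no supplied document confirms are held.

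**Downside.** Transfers and prescriber stops may be scored as poor adherence, the addition comes after results were known, and the two analyses need not bracket the truth. In the last row of the table, both could show 0 if recorded coverage is alike in the two arms, while the true difference is -7.4 points.

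### Does the missing end date on the two-refill rule leave the primary analysis set and the 10% imputation trigger unsettled?

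*SAP*

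**What the plan says.** The SAP's intention-to-treat text has four relevant statements.

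- The general sentence keeps participants in their assigned group, "assuming they have enough information to calculate the outcome".
- The second bullet includes "the outcomes for each participant having at least 2 post-enrollment medication refills (required for primary outcome calculation").
- The third bullet begins "The primary analyses will be reported for all participants having 2 medication refills post-enrollment".
- It continues "If the amount of missing data exceeds 10% at the primary endpoint, missing data will be imputed", assuming missing at random.

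The refill count therefore starts at enrollment, and the SAP names no end. It does not say what the 10% is a percentage of.

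The Protocol, under Inclusion/Exclusion Criteria, says "patients with 2 or more refills in the study period will be included in the data analysis". It does not define that period.

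The Protocol's Background gives the time points: "The primary outcome of the QI study was PDC calculated at 8-months post-enrollment", and "An exploratory analysis evaluated PDC at 6-months and 12-months post-enrollment". All three are tested: "A Wilcoxon test was used to test the difference in 6, 8, and 12-month post-enrollment PDCs".

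**The concern.** A count with a start and no end does not fully define an analysis set when the outcome is measured at three times. The Protocol's study period could mean the calendar period from May 2019 to August 2021, the 8 months of pharmacist follow-up, or the 12-month outcome window. The calendar reading would also give patients unequal windows, depending on when they enrolled.

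Two features of the SAP make this look like more than loose drafting.

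1. If the count closes at month 8, everyone in the set has the refills that the SAP says the primary outcome needs. Nobody in the set can then be missing that outcome for too few refills, and the 10% rule seems to have nothing to act on.
2. A patient whose second refill comes in month 10 seems to be out of the 12-month test if the primary-outcome rule is read at month 8, and in it under the general sentence about having enough information.

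At stake are which randomised patients are analysed and whether the primary analysis uses observed or imputed data. Few refills is itself a form of low adherence, so membership of the set is related to the outcome. The Protocol also says the results are already known to be positive, which makes a choice left open less comfortable.

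**Working it through.** **Inputs.** From the documents: at least two post-enrollment refills, outcomes at 6, 8 and 12 months, primary at 8, trigger above 10%. The documents give no days' supply, refill rate, adherence level or sample size. There is no stated figure to reproduce, and every percentage below is an illustration.

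**Reading the text.** The second bullet calls the two refills necessary for the primary outcome, and the Protocol places that outcome at 8 months. Together they point to month 8 for the primary test. The general sentence covers all quantitative outcomes and asks for enough information for the outcome in question. Applied outcome by outcome, this means two refills within that outcome's own window. The month-10 patient then has no 8-month value and does have a 12-month value. Neither SAP sentence is broken, because that patient does have two post-enrollment refills.

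**Who could be affected (evenly spaced refills).** Let the gap be g = days' supply / PDC, with the first refill uniform on (0, g) and the second one gap later. Then P(second refill by day w) = (w − g)/g, held between 0 and 1. With w = 243 days (month 8), a patient can fall short only if g > 243/2 = 121.5 days.

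- 30-day fills: PDC below 30/121.5 = 24.7%.
- 90-day fills: PDC below 90/121.5 = 74.1%. For example, PDC 0.6 gives g = 150 and (243 − 150)/150 = 0.62.

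Averaging over beta-distributed PDC (mean 0.6 to 0.8, SD 0.15 to 0.20, 2,000,000 simulated patients per case), the share of a month-12 set without two refills by month 8 is:

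| Share of patients on 90-day fills | Range |
|---|---|
| None | 0 to 1.7% |
| Half | 4.5 to 16.4% |
| All | 9.0 to 34.1% |

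At mean 0.8 the all-90-day share is 9.0% with SD 0.15 and 10.3% with SD 0.20, so even there the 10% line can be crossed.

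**How the denominator acts (random refills).** If refills follow a Poisson process with mean gap g, P(at least 2 by t) = 1 − exp(−t/g)(1 + t/g). For g = 90, this is 0.751 at t = 243 and 0.912 at t = 365. The share lacking two refills by month 8 is then 1 − 0.751 = 24.9% of all recruited and (0.912 − 0.751)/0.912 = 17.7% of the month-12 set.

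| Mean gap (days) | Month-8 set | Month-12 set | All recruited |
|---|---|---|---|
| 40 | 0% | 1.5% | 1.6% |
| 60 | 0% | 7.3% | 8.8% |
| 75 | 0% | 12.7% | 16.6% |
| 90 | 0% | 17.7% | 24.9% |
| 120 | 0% | 25.6% | 39.9% |

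In this table the month-12 and all-recruited denominators agree on which side of 10% they fall. They can disagree when refill rates vary between patients. With gamma-distributed rates (shape 2, mean rate one refill per 45 days) the shares are 8.6% and 18.0%.

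**What the trigger can refer to.** The zero column follows from the definition and covers only too few refills. The trigger is not limited to that cause. It can cover an 8-month value missing for another reason. It can also be read against everyone recruited, since the first bullet says outcome data are collected on all of them. On either reading the rule has something to act on.

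**The case for a change.** The strongest opposing case is that the natural reading does not answer everything. Accepting month 8 for the primary test still leaves the 10% without a denominator, and the figures above show that the denominator alone can decide whether imputation is used. A written definition would cost a few sentences and a row of counts from data already held. With results known, it is better to have the rule on paper than to infer it.

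Most of this stands as description: the denominator and the meaning of missing are not stated, and stating them would be tidier. It falls short of a reason to change the plan on three counts.

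- The plan, followed sensibly, is not shown to give a wrong answer. If no patient has a second refill between months 8 and 12, closing the count at month 8 or month 12 gives the same primary set.
- The data were collected under an earlier IRB approval, cited in the Protocol's Study Procedures, and its plan is not among these documents. It may already fix the window. Writing a new rule now, with results known, would not have the standing of a prospective one.
- The one substantive alternative, holding the 6- and 12-month tests to the month-8 set, has a real cost. It drops patients whose 12-month value can be calculated and whom the SAP's general sentence keeps. It also leaves patients without two refills by month 6 in the 6-month comparison. That is a disputable trade-off, with no clear gain.

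**Conclusion.** The gap is real but minor, and no change follows. Month 8 is the natural window for the primary test, and a window matched to each outcome reconciles the SAP's sentences. The trigger is unspecified in detail but does not contradict the analysis set. An analyst would count refills to month 8 for the primary test and, in the ordinary course of reporting, show per arm how many patients were randomised and how many had a calculable value at each time.

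The possible effect on the trigger runs from negligible (at most 1.7% if all fills are 30-day) to well above 10% (up to 34.1% if all are 90-day). These figures rest on assumed refill spacing, days' supply and adherence levels, none of which the documents give. No effect on the primary estimate or p-value is shown. This conclusion concerns only the refill window and the denominator. It does not judge whether limiting an intention-to-treat analysis to patients with two refills, or imputing under missing at random, is sound.
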